1.0 Project Summary/Abstract

Latinas suffer disproportionately from breast cancer relative to non-Latina Whites (NLWs), including late stage detection. While there have been controversies in breast cancer screening, non-adherence to guideline-concordant screening continues to be a modifiable determinant of breast cancer outcome disparities. Thus, increasing participation in breast cancer screening among Latinas, especially care that corresponds with clinical and academic guidelines, is a public health priority.

Participatory approaches are popular methods to improve screening within this group and have included approaches that deliver education to non-adherent Latinas and train motivated community members' interventions (community health workers, breast cancer survivors) to engage in breast health promotion. The latter approach, empowerment interventions, concern training participants to engage in social outreach (e.g., having conversations with family and friends about breast health) and volunteering (e.g., helping in health fairs, engaging in civic campaigns about breast cancer programs). Patient activation and volunteerism literature suggest that empowerment interventions may have 'added value' over delivering education in terms of preventive health psychosocial factors and practices. Relative to education interventions, empowerment interventions may also affect women's networks, as they may be more likely to lead to disseminate evidence-based breast health promotion among their family and friends. To date, little research has compared interventions' effects on individual-level outcomes or used formal social network analysis to examine network effects.

The proposed work adds to the literature through conducting a trial to compare the two approaches (education versus empowerment) on three sets of outcomes: 1) women's own screening, 2) women's own self-efficacy, norms, support, knowledge; and 3) women's networks (measured by egocentric analysis). We will recruit 150 Latina women to participate in the Intervention. 75 women will be recruited from The Resurrection Project and 75 women will be recruited from Centro Comunitario Juan Diego.

We will be conducting educational classes at the two participating sites. We will also administer several surveys at different sessions. The variations in the implementation of Phase 3 will be the Workshops at each site. Each site will conduct a Breast Cancer Education session. However, TRP will conduct Communication and Volunteerism workshops, whereas Juan Diego will conduct Diet and Physical Activity workshops. The Intervention is broken down into 3 sessions at each site across 3 consecutive weeks. Each session will be held with 5-8 recruited participants. We will hold 5 – 9 sessions at each participating site for three consecutive weeks.

Ancillary studies and analytic studies include: 1) qualitative data collection with participants' family and friends (Phase 4); 2) cost data collection and cost-effectiveness analysis (Phase 5); and, 3) community volunteerism data abstraction (e.g., preferences regarding events; number of contacts; barriers, if any, during contact; decisions/solutions made, if any during contact; interest in event participation; type of event; and attendance at event) and secondary analysis of Phase 3 volunteerism data (Phase 6). During Phase 7, 20 former intervention participants will participate in focus groups to provide their perspectives on their experiences and suggestions for future interventions.

2.0 Background/Scientific Rationale

Multiple community-based participatory research (CBPR) interventions exist that have sought to improve breast cancer screening among Latinas. For example, there have been >10 CBPR education breast cancer screening interventions for Latinas using community health workers (CHW).⁹ Participants were breast health promotion recipients. As well, there are few CBPR empowerment interventions strove to build community infrastructure to improve screening among Latinas.²⁵⁻²⁸ Participants were trained to become breast health promotion agents in social outreach (e.g., how to discuss breast health information) and volunteerism (e.g., how to participate in health fairs and policy).

Of which we are aware, no study has compared the relative efficacy of these interventions. First, with regard to screening uptake, empowerment interventions may result in greater screening than education interventions, given documented benefits of patient activation and volunteerism in other disease models.^{16-20,35} Second, activating Latinas to become breast health promotion agents may lead to interest and skills for monitoring evidence, resulting in lay individual knowledge that is longitudinally concordant with academic and clinician recommendations. Promoting social outreach and volunteerism may also lead to greater exposure to informed peers, resulting in more sustained perceived social norms, support, and self-efficacy associated with guideline-concordant screening. Third, empowerment interventions are effective in reaching participants' networks and broader communities and may be more effective in reaching networks than education interventions due to intervention materials specific to teaching women how to engage in social outreach.

Toward the goal of addressing these gaps in the literature, we will conduct a trial that compares education and empowerment interventions on these outcomes.

3.0 Objectives/Aims

The primary goal of this proposed work is to develop materials and conduct a trial that would examine the relative efficacy of education and empowerment interventions to improve breast cancer screening among Chicago-based Latinas. With regard to our objectives, we proposed to:

Aim 1: Develop and compare the efficacy of a breast health empowerment intervention on guideline-concordant screening compared to an education intervention, using an area-level treatment control group design with a community-based sample of 150 Latinas. The empowerment arm will include breast health and empowerment information (e.g., how to begin conversations, where to volunteer). The education arm will include only breast health information. Content draws from my team's existing materials. Hypothesis: Empowerment participants will have increased screening compared to education participants.

Aim 2: Compare interventions' effects on psychosocial facilitators of screening across six months. Hypothesis: Empowerment participants will have sustained increases in self-reported self-efficacy, norms, support, and knowledge about breast cancer screening compared to education participants.

Aim 3: Compare interventions' network effects through egocentric network analysis. Hypothesis: Empowerment participants will have greater social connectedness related to breast health and network size and will have referred a greater number of peers to participate in the study compared to education participants.

Aim 4: Characterize intervention effects on family and friends of intervention participants.

Aim 5: a) Determine the incremental costs for each additional woman screened for the empowerment approach relative to the education approach, combining new cost data with existing effect measures in our trial. Hypothesis: The empowerment intervention will have low incremental costs for each additional woman screened, especially when including indirect effects. b) Use those data and published literature to compare approaches in terms of achieving HP2020 goals and costs for additional life-years gained across 10 years, using existing simulation platforms. Hypothesis: The empowerment intervention will be more cost-effective than the education intervention in terms of life years gained.

Aim 6: a) quantify the relative effects of education and empowerment interventions on intention to volunteer, volunteerism behaviors, intention to participate in civic engagement, and civic engagement behaviors; and, b) characterize the feasibility of a community-based civic engagement and community development navigation program for Latinas.

Aim 7: Characterize the perspectives and experiences of intervention participants, based on focus groups (n=20).

Toward that goal, we will first run semi-structured focus groups with 20 Latinas who will not be eligible for the future trial and 10-15 CHW/CHV/promotoras who would be eligible to deliver the intervention in order to: 1) identify relevant topics to incorporate into interventions; and 2) examine circumstances that may facilitate implementation. No contact information on women who have participated in any previous focus groups or will we re-contact any woman who has already participated in a focus group for future trial. We will only invite new recruits for each focus group that is held. This phase of the project will be called Phase 1.

We will then create materials based on this feedback and consultation from the UIC CCTS Community Engagement Advisory Board.

Next, we will run semi-structured focus groups with a second set of 20 Latinas who would be eligible for the future trial and 10-15 CHW/CHV/promotoras who would be eligible to deliver the intervention in order to 1) verify the appropriateness and logic of the updated material; and 2) identify alternative content areas and approaches. This phase of the project will be called Phase 2.

To date, we have worked on the first part of Aim 1 through Phases 1 and 2. Specifically, with regard to development, we ran semi-structured focus groups with 20 Latinas who will not be eligible for the Phase 3 (i.e., Intervention Implementation) and 10-15 CHW/CHV/promotoras who would be eligible to deliver the Phase 3 Intervention in order to: 1) identify relevant topics to incorporate into interventions; and 2) examine circumstances that may facilitate implementation. This phase of the project will be called Phase 1. We created materials based on this feedback and consultation from the UIC CCTS Community Engagement Advisory Board. Finally, we ran semi-structured focus groups with a second set of 20 Latinas who would be eligible for the future trial and 10-15 CHW/CHV/promotoras who would be eligible to deliver the intervention in order to 1) verify the appropriateness and logic of the updated material; and 2) identify alternative content areas and approaches. This phase of the project was called Phase 2. We completed the semi-

structured Phase 1 and Phase 2 focus groups. Data from these activities was used to develop Phase 3 Invention materials.

We will now work on implementing the intervention and assessing changes across interventions with regard to Aims 1-3 outcomes (screening, psychosocial facilitators, network effects). We plan on recruiting 150 Latina women to participate in the Intervention. 75 women will be recruited at The Resurrection Project and 75 women will be recruited from Centro Comunitario Juan Diego. No contact information on women who have participated in any previous focus groups or will we re-contact any woman who has already participated in a focus group for future trial. We will only invite new recruits for the intervention. We will be conducting educational classes and workshops at the two participating sites. The Intervention is broken down into 3 sessions at each site across 3 consecutive weeks. Each session will be held with 5-8 recruited participants. We will hold 5 – 9 sessions at each participating site for three consecutive weeks until we reach our target population of 150 Latina women. The variations in the implementation of Phase 3 Intervention will be the Workshops at each site. Besides each site conducting a Breast Cancer Education session at Session 1, TRP will conduct Communication and Volunteerism workshops at Session 1 and 2. Juan Diego will conduct Diet and Physical Activity workshops at Session 1 and 2. Our outcomes will be measured by Surveys assessed during Session 1, Session 3, and six months post-participation in workshops for 20-30 minutes. At the end of Phase 3, participants who have agreed to be contacted again will be contacted by study staff by phone and given the opportunity to learn about preliminary analyses. Participants will be offered information regarding preliminary analyses of the study. They will have the opportunity to decline learning about study results without any negative impact/costs to their relationships with the study sites or UIC. Script for these calls was submitted as part of Amendment #24.

For Aim 4, we will conduct 20 interviews with family and friends of intervention participants (10 affiliated with empowerment participants, 10 affiliated with education participants). Phase 4 participants will be 18 years or older, have not participated in the study, and identify as family/friends of intervention participants. These individuals will be recruited by Phase 3/intervention participants. Phase 3 participants will learn about the opportunity to recruit individuals for Phase 4 when they learn about the opportunity for peer referral in workshops. Phase 3 participants who have completed the intervention sessions will learn about the opportunity during booster calls. Each interview will take place where the participant prefers, will be in the language the participant prefers (English/Spanish), will be audio-recorded, and will take approximately 1-hour.

For Aim 5, cost data will be collected from community-based organization (personnel and non-personnel costs), participant (costs for intervention participation, knowledge transfer, receipt of screening), and healthcare system perspectives (direct medical costs). This information will be collected from surveys as well as from different observational records (participant encounter logs, behavioral logs). The incremental costs will then be combined with the trial's effects measurement, which include direct (additional # of participants screened) and indirect effects (additional # of participants' family and friends screened). We will conduct one-way sensitivity analyses to identify cost and effect drivers. To note, Aim 5 will not involve any new participants – only Phase 3 participants who complete informed consents with information about Aim 5 (up to 80-82 participants). All of these data will also inform a subsequent simulation model, which will include inputs from published literature as well as data collected through data described above.

For Aim 6, secondary analyses will be conducted of Phase 3 data and community data for Phase 3 participants who agree to the release of their data from partners' existing community volunteerism databases (e.g., if they were called by community partners, if they agreed to participate, if they attended).

For Aim 7, we will run semi-structured focus groups with 20 Latinas who participated in our intervention in order to understand their experiences and recommendations for future interventions. We will only invite women who have previously participated and have provided permission for re-contact.

There will be a total of 300 participants enrolled in our study, including Phase 1 and 2 participants (40 Latinas, 15-30 community health workers), Phase 3 and 5 participants (240 Latinas who enroll, of which 150 estimated to complete entire study), and Phase 4 participants (20 family/friends).

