Educational Sessions will be attended by the UIC Staff/Staff at Centro Comunitario Juan Diego /Staff at The Resurrection Project and will be located in Centro Comunitario Juan Diego offices or other community venues chosen by Centro Comunitario Juan Diego within the target neighborhoods. Empowerment Sessions will be attended by the UIC Staff/Staff at Centro Comunitario Juan Diego /Staff at The Resurrection Project and will be located in The Resurrection Project offices or other community venues chosen by The Resurrection Project within the target neighborhoods. UIC staff will be in contact with the participants and the participating site community health workers during the entire Intervention period. Community Health Workers from each participating site will conduct the educational sessions and the workshops. UIC staff will administer all the surveys and Informed Consent. Educational Sessions will be conducted in either Spanish or English and participants will have the choice of attending one in the language format they choose. Prior to the start of the sessions, UIC staff will discuss Informed Consent with participants who will be asked to sign a written informed consent if they wish to participate. UIC staff will meet with the women who have consented and who have agreed to attend the 3 sessions and workshops for the duration of the Intervention activities that will be held once a week for three consecutive weeks.

Prior to the start of the Session 1 Session at each site and after Informed Consent is given, participants will be asked to complete Survey 1 (T1), which includes demographics (years in US, country of birth, income, education, marital status, age – NOT DOB), volunteerism history, social interactions, breast cancer beliefs (cultural beliefs, perceived risks, norms and social interactions concerning breast cancer) and breast cancer screening variables.

During the Phase 3 Intervention, the Community Health Worker at each site (TRP and Juan Diego), will conduct the session. UIC student/staff will be present at each activity and will administer the Informed Consents as well as will help Community Health Workers as is needed.

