9.0 Data Analysis Qualitative

For **Phase 1, 2, 4 and 7**, [name] and her team [Appendix P] will lead content analyses with inductive and deductive approaches[53, 54] in Atlas.ti.[55] She and two UIC students [TBA] will read transcripts and generate codes. We will compare notes, review data, cluster similar ideas into representative themes, and discuss areas of disagreement until consensus is reached. A final codebook will be used for re-analysis. Sample sizes are within the recommended range to meet thematic saturation.[53,54]

Quantitative

For **Phase 3**, our project will include 3 sets of analyses to examine the 3 outcomes – breast cancer screening, psychosocial facilitators (self-efficacy, norms, support, and knowledge), and social network dissemination. All analyses will be conducted in statistical packages (SPSS, SAS, R).

We will use multiple imputation techniques to handle missing data.⁶⁵ Measures will be assessed and included if they have adequate reliability (Cronbach's $\alpha \geq 0.70$). We will first conduct descriptive statistics. We will identify covariates based on theory and bivariate analyses to examine 1) intervention differences in demographic, healthcare, and pre-study factors (e.g., screening history) and 2) the relationship of these factors to each other and outcomes (e.g., screening). We will conduct a multivariable logistic regression to examine study arm differences in guideline-concordant screening six months after participating in interventions. We will conduct sensitivity analyses, using only women 1) with complete medical record data and 2) recruited by Study Site staff. Based on power analyses to estimate the minimal detectable effect of study arm differences among 150 Latinas on screening, $p < .05$, power = .80 and two-tailed tests, we would be able to detect a medium/large effect in a logistic regression (OR = 2.8).

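### Each arm is delivered at a single site, so the Aim 1 odds ratio cannot separate the programme effect from unmeasured site or deliverer differences, and the plan does not say so

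*Combined protocol and SAP*

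**What the plan says.** The stated goal in section 3.0 is to "examine the relative efficacy of education and empowerment interventions". Aim 1 names the design, "using an area-level treatment control group design", with 150 women. It adds a directional hypothesis that empowerment participants will be screened more.

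Arm is defined by place:

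- **Content** (section 1.0): "TRP will conduct Communication and Volunteerism workshops, whereas Juan Diego will conduct Diet and Physical Activity workshops".
- **Venue** (section 6.2, Phase 3): empowerment sessions "will be located in The Resurrection Project offices or other community venues chosen by The Resurrection Project within the target neighborhoods"; education sessions "will be located in Centro Comunitario Juan Diego offices or other community venues chosen by Centro Comunitario Juan Diego within the target neighborhoods".
- **Deliverer** (section 6.2, Phase 3): "Community Health Workers from each participating site will conduct the educational sessions and the workshops".
- **Sample** (section 6.1, Recruitment – Phase 3): convenience sampling, 75 women from each organisation. No random allocation of women or sites is described.

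For the primary outcome, section 9.0 says "We will conduct a multivariable logistic regression to examine study arm differences in guideline-concordant screening", measured six months after participation. Covariates come from theory and bivariate analyses of demographic, healthcare and pre-study factors. Two sensitivity analyses restrict the sample: to women with complete medical records, and to women recruited by site staff. Sections 9.0 and 12.1 give a minimal detectable OR of 2.8 for 150 women (two-sided 0.05, power 0.80). Neither section mentions that arm coincides with site.

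**The concern.** With two sites and two arms, every feature that differs between the organisations differs in exactly the same way between the arms. That includes the health workers, the venues, and the mix of women who respond to each organisation. If women at one site would have been screened more often under either programme, the regression credits the gap to the programme unless measured covariates happen to capture it. Aim 1 has no baseline outcome to subtract, because section 4.1a admits only women without a mammogram in the last two years.

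At stake is what the trial can conclude. A significant OR would answer whether the two site-delivered programmes differed. It would not answer whether empowerment content works better than education content. The same effect then enters the trial-based cost-effectiveness ratio in Aim 5.

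**Working it through.** **1. Can any planned model separate arm from site?**

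A design matrix with columns for intercept, arm and site has 3 columns but rank 2, with an arm–site correlation of 1.0. Between-site degrees of freedom are 2 sites − 2 arms = 0, so site variance cannot be estimated.

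| Planned analysis (section 9.0) | Effect on the arm–site link |
|---|---|
| Aim 1 logistic regression with covariates | Adjusts measured individual factors; link remains |
| Aim 1 sensitivity subsets | Fewer women, still one site per arm |
| Aim 2 mixed model (surveys within women) | Arm\*time removes stable site differences in level; still aliased with site\*time |
| Aim 3 regression or mixed model | Clustering considered is of the peer-referral kind; link remains |
| Phase 6a clustering by cohort/group | Cohorts sit inside sites; link remains |

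**2. The plan's own figure, OR = 2.8.**

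Inputs from section 9.0 are N = 150 (75 per arm), two-sided 0.05 and power 0.80. The control screening rate is not given, so I scanned it. At 19%, the odds are 0.19/0.81 = 0.2346; multiplying by 2.8 gives 0.6568, or 39.6%. The pooled two-proportion formula then gives power 0.799. A 60% control rate gives 0.802. So 2.8 is plausible, but only for 150 independent women with no site variance.

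With a site intraclass correlation (ICC, assumed), the design effect is 1 + 74 × ICC. At the 19% control rate:

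| ICC | Design effect | Effective n per arm | Power for OR 2.8 |
|---|---|---|---|
| 0 | 1 | 75 | 0.80 |
| 0.005 | 1.37 | 54.7 | 0.66 |
| 0.01 | 1.74 | 43.1 | 0.56 |
| 0.02 | 2.48 | 30.2 | 0.42 |

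These powers suppose the ICC is known. With two sites it cannot be estimated.

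**3. False-positive rate if sites vary (all inputs assumed).**

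Take 20% screened, 75 per arm and no intervention effect. The standard error the model uses is √(2 × 0.2 × 0.8 / 75) = 0.0653. The true standard error is √(0.0653² + 2 × SD²). The rejection rate is 2 × P(Z > 1.96 × 0.0653 / true SE).

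| Site SD | True SE | Effective cut-off | Rejection rate |
|---|---|---|---|
| 0.03 | 0.0779 | 1.644 | 0.100 |
| 0.05 | 0.0963 | 1.330 | 0.184 |
| 0.07 | 0.1186 | 1.079 | 0.280 |

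These SDs correspond to ICCs (SD²/0.16) of 0.006, 0.016 and 0.031. The design-effect formula gives 0.094, 0.137 and 0.213 at ICCs of 0.005, 0.01 and 0.02. A beta-binomial simulation at 20% screened gives 0.084, 0.126 and 0.201.

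**4. A fixed gap between these two sites (assumed).**

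For 20% versus 30% with no intervention effect, the expected OR is (0.3/0.7)/(0.2/0.8) = 1.71, and the test rejects 29% of the time. For 30% versus 40%, the OR is 1.56 and the rejection rate 25%.

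**5. How much site difference would explain an observed OR of 2.8?**

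Take 19% versus 39.6% as the observed rates. The difference is 20.6 points, with standard error √[(0.19 × 0.81 + 0.396 × 0.604)/75] = 0.0724. The 95% lower limit is 20.6 − 1.96 × 7.24 = 6.5 points. A pre-existing site difference of about 6.5 points would move that limit to the null. Subtracting 10 points leaves 29.6% versus 19%, OR 1.80; subtracting 15 leaves 24.6% versus 19%, OR 1.39.

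**The case against.** The design is declared openly, and two partner organisations may be all that a community project has. Section 3.0 states a goal and a hypothesis, not a conclusion. A reader might infer that the plan commits itself to a causal efficacy claim, but the documents never say how results will be worded. That stands. The point is that the limitation is missing, at a stage when adding it is cheap.

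A reader might also infer that the sites serve separate neighbourhoods with different clinic access. The documents do not show this. Section 4.1a lists four eligible neighbourhoods without assigning any to a site, section 5.1 has flyers at both organisations and across all target areas, and clinic access is not described. What is documented is separate venues, deliverers and recruitment totals.

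It is also too strong to say that every site difference will be reported as an intervention effect. The covariate step in section 9.0 compares healthcare and pre-study factors between arms, and so between sites, and can remove measured individual differences. It cannot reach unmeasured or deliverer effects.

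Lastly, the two organisations are fixed rather than drawn at random, so the problem is confounding bias, and the type I rates only illustrate its scale. That is fair; step 4 gives the fixed-gap version. Nor is non-randomised allocation essential to the argument: how programmes were assigned to sites is not stated, and a coin toss between two sites would leave the same aliasing.

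**Conclusion.** The point holds for Aim 1 on structure alone, without any assumed figure: no listed model, subset or clustering term separates programme from site. The size is unknown, because the documents give neither a screening rate nor a site variance. On the assumed ranges it is large enough to matter: ordinary-looking site gaps can double the nominal error rate or more, and a gap of 10 points can yield an OR above 1.5 with no programme effect.

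It should not be carried unchanged to the other aims. Aim 2 is better protected, because change from baseline removes stable level differences. Section 12.1 calls the Phase 5 cost-effectiveness analysis exploratory, and its simulation also draws on published estimates. The trial remains informative; the estimand and its wording need restating.

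**What to change.** 1. **Sections 3.0 and 9.0, Aim 1.** Define the arm coefficient as the covariate-adjusted difference between two site-delivered programmes (programme plus site), and describe it as an association rather than efficacy.
2. **Sections 9.0 and 12.1.** State that OR = 2.8 assumes independent women and no site variance, and give the control screening rate used.
3. **Section 9.0, Aim 1.** Report a bias analysis beside the OR: the OR and its confidence interval after assumed pre-existing site differences of, for example, 0 to 15 percentage points, together with the difference that would move the estimate, and the one that would move its confidence limit, to the null. Fix the range before analysis.
4. **Aim 2.** State that arm\*time removes stable site differences in level but remains aliased with site\*time.
5. **Aim 3.** Carry the programme-plus-site caveat.
6. **Aim 5.** Carry the range of Aim 1 effects from item 3 into the sensitivity analysis of the trial-based incremental cost-effectiveness ratio.

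The cost is wording and one simple calculation, with no new sites, women or data. The downside is a weaker headline claim. None of this separates programme from site; that would need several sites per arm or both programmes at each site.
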